Emerging evidence suggests that although maternal antibodies are transferred to infants transplacentally after maternal vaccination, titers wane over the course of the first 6 months of life and are undetectable in up to 43% of infants at 6 months of age, supporting the need for early vaccination in this age group (Shook et al 2022). While observational data (Halasa et al 2022) demonstrate that maternal vaccination during pregnancy can be 61% effective (95% CI = 31%-78%) in preventing hospitalization of infants aged < 6 months, there are no systematic studies of the need and risk-benefit of infant immunization against COVID-19. Additionally, it remains unknown if transferred passive immunity after maternal immunization with vaccines targeting prototype SARS-CoV-2 confer benefit of protection against emerging variants to the infants. Hence, there remains a need for active immunization strategies in this age group.

In the ongoing Study mRNA-1273-P204 (data snapshot on 21 Feb 2022), the safety profile of the 2 dose primary series in children and toddlers/infants (6 months to < 6 years of age) was generally consistent with the known safety profile observed in other studies of mRNA-1273. In addition, the events commonly seen in this pediatric population consisted primarily of grade 1 and grade 2 reactogenicity occurring within 2 days after either dose lasting 2 to 3 days. Solicited local and systemic ARs in children 6 months to < 6 years of age were generally consistent with the AE profile of mRNA-1273 in older age groups with the exception of fever. Fever was most commonly reported on Day 1 or Day 2 after any vaccination and lasted for a median duration of 1 day. Beyond Day 2 (after any dose) fever rates were similar between the mRNA-1273 group and the placebo group. Although no studies to date have evaluated mRNA-1273.214 in young children, ongoing trials in adults have not raised any safety concerns. Based on experience to date, the risk-benefit profile of evaluating mRNA-1273.214 in younger children is favorable.

Protocol: mRNA-1273-P206, Original

The objective for this Phase 2 study is to evaluate the safety, tolerability, reactogenicity, and effectiveness of 2 dose levels (5 and 10 μ g) of mRNA-1273.214 vaccine or another modified vaccine (both referred to as 1273.214 in the document) administered as 2 doses 8 weeks apart in participants aged 12 weeks to < 6 months.

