9.5. Statistical Analyses

9.5.1. Immunogenicity Analyses

The primary analysis population for immunogenicity will be the PPIS-Neg, unless specified otherwise. The primary objective of Part 2 of this study is to use the immunogenicity response to infer effectiveness of mRNA-1273.214 vaccine administered as 2 doses 8 weeks apart in infants aged 12 weeks to < 6 months at the dose level selected for investigation.

Immunogenicity Analyses for mRNA-1273.214 Primary Series

Immune response as measured by GMT value and SRR in the infant group based on Ab levels will be compared to that in adult (≥ 18 years of age) participants from Study mRNA-1273-P301 using Ab data. The immunogenicity data from participants who are assigned to the same dose level in Part 1 and Part 2 of this study may be combined for the immunogenicity analyses.

To assess the difference in immune response between the infant participants in Study mRNA-1273-P206 at 28 days after the last dose of mRNA-1273 primary series compared to the adult (≥ 18 years of age) participants in Study mRNA-1273-P301 at Day 57, an analysis of covariance model will be carried out with Ab as dependent variable and a group variable (an mRNA-1273 arm/group of Study mRNA-1273-P206 versus participants in Study mRNA-1273-P301) as the fixed variable for each participant arm/group, the analysis may adjust for key characteristics such as age, sex, etc. The GMT value of mRNA-1273.214 arm at 28 days after the last dose of mRNA-1273.214 primary series and GMT value of mRNA-1273 at Day 57 (28 days after the second dose of primary series) in Study mRNA-1273-P301 will be

Protocol: mRNA-1273-P206, Original

estimated by the GLSM from the model. The GMR (which is calculated as ratio of GMT) will be estimated by the ratio of GLSM from the model. The corresponding 2-sided 95% CI of GMR will also be provided.

The noninferiority of GMT of mRNA-1273.214 primary series compared with mRNA-1273 primary series will be considered demonstrated if:

• The lower bound of the 95% CI of the GMR (the infant participants in Study mRNA-1273-P206 at 28 days after the last dose of mRNA-1273.214 primary series, compared with the participants in Study mRNA-1273-P301 at Day 57) > 0.67 based on the noninferiority margin of 1.5.

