4.3. Sample Size and Power

In Part 2, approximately 600 infant participants 12 weeks to < 6 months of age will be enrolled at the dose level selected for Part 2, with an mRNA-1273.214 to placebo ratio of 1:1. Assuming 10% to 15% participants are not negative SARS-CoV-2 status at baseline, it is estimated that there will be a minimum of approximately 250 evaluable participants in the mRNA-1273.214 arm eligible for immunogenicity analyses.

The sample size of approximately 300 infant participants in the mRNA-1273.214 arm in Part 2 is considered to be sufficient to support a safety assessment. There is at least 90% probability to observe at least 1 participant with an AE at a true AE rate of 1% in this group.

The sample size calculation for each of the 2 primary noninferiority hypothesis tests (H_A^1 and H_A^2) was performed, and the larger sample size was chosen for the study.

• With approximately 250 evaluable participants receiving mRNA-1273.214 in the Per-Protocol Immunogenicity Subset - Negative (PPIS-Neg) in Study mRNA-1273-P206 and adults (≥ 18 years of age) in Study mRNA-1273-P301, there will be at least 90% power to demonstrate noninferiority of the immune response against Omicron variant, as measured by the geometric mean concentration (GMC) or GM level, in infant population at a 2-sided alpha of 0.05, compared with that in adults (≥ 18 years of age) in Study mRNA-1273-P301 receiving mRNA-1273, assuming an underlying geometric mean ratio (GMR) (which is calculated as ratio of GMC or

- GM level) value of 1 and the standard deviation of the natural log-transformed concentration/level is assumed to be 1.0, and a noninferiority margin of > 0.667.
- With approximately 250 evaluable participants receiving mRNA-1273.214 in the PPIS-Neg in Study mRNA-1273-P206 and adults (≥ 18 years of age) in Study mRNA-1273-P301, there will be at least 90% power to demonstrate noninferiority of the immune response against Omicron variant as measured by SRR in infants at a 2-sided alpha of 0.05, compared with SRR against Omicron variant in adults ≥ 18 years of age in Study mRNA-1273-P301 receiving mRNA-1273, assuming SRR of 60% to 70% in Study mRNA-1273-P301, true SRR improvement of 10% in infants from Study mRNA-1273-P206 compared with adults from Study mRNA-1273-P301, and a noninferiority margin of 5%.

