- b) study day on or after the date of the first injection but before the second injection (if applicable) will be calculated as: date of assessment/event date of the first injection + 1;
- c) study day on or after the date of the second injection will be calculated as: date of assessment/event date of the second injection + 1; if study day is on the same day as the second injection, date and time will be compared with the second injection date and time. If time is prior to the time of second injection, then study day is calculated as: date of assessment/event date of the first injection + 1; If it is after the time of second injection or the time is missing or not available then study day is calculated as: date of assessment/event date of the second injection + 1.

For calculation regarding antibody levels/concentrations, antibody values reported as below LLOQ will be replaced by 0.5 × LLOQ. Values that are greater than the upper limit of quantification (ULOQ) will be converted to the ULOQ if actual values are not available, and actual values will be used if available. Missing results will not be imputed.

The following analysis periods or stages for safety analyses will be used in this study:

- Up to 28 days after any vaccination: this stage starts at the day of each vaccination and continue through the earliest date of (the day of each vaccination and 27 subsequent days, next vaccination [if applicable]). This analysis period will be used as the primary analysis period for safety analyses including unsolicited AE, except for solicited AR, unless specified otherwise.
- Overall period (throughout the study): this analysis period starts at the first injection on Day 1 and continues through the earliest date of (study completion, discontinuation from the study, or death).

Unscheduled visits: Unscheduled visit measurements will be included in analysis as follows:

- In scheduled visit windows per specified visit windowing rules.
- In the derivation of baseline/last on-treatment measurements.
- In the derivation of maximum/minimum on-treatment values and maximum/minimum change from baseline values for safety analyses.
- In individual subject data listings as appropriate.

Visit windowing rules: The analysis visit windows for protocol-defined visits are provided in Appendix B.

Incomplete/missing data:

- Imputation rules for missing prior/concomitant medications, non-study vaccinations and procedures are provided in Appendix C.

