6.4.3. Primary Analysis of Antibody-Mediated Immunogenicity Endpoints

For Part 2, the immune response as measured by the serum Ab GM value and SRR against SARS-CoV-2 VOC (Omicron) at 28 days after the second dose of mRNA-1273.214 will be compared to that of the young adult participants (18-25 years) at 28 days after the second dose of mRNA-1273 primary series in Study mRNA-1273-P301.

An analysis of covariance (ANCOVA) model will be carried out with the serum Ab value at 28 days after the second dose of IP (Day 85 for Study P206, Day 57 for Study P301) as the dependent variable and a group variable (mRNA-1273.214 vs. mRNA-1273) as the fixed variable, adjusted by the baseline serum Ab value. The serum Ab GM value at Day 85 for Study P206 and serum Ab GM value at Day 57 for Study P301 will be estimated by the geometric least square mean (GLSM) from the model. The GMR (Study P206 vs. Study P301) will be estimated by the ratio of GLSM. Its 2-sided 95% CI will also be provided to assess the difference in immune response between the Study P206 and Study P301 at 28 days after the second dose of IP.

The noninferiority of the GM value of mRNA-1273.214 compared with mRNA-1273 primary series will be demonstrated if the lower bound of the 95% CI of the GMR > 0.667.

In addition, the serum Ab GM value with its 95% CI and GMR with 95% CI will be provided at 28 days after the second dose of IP. The 95% CIs will be calculated based on the t-distribution of the log-transformed values then back transformed to the original scale. Descriptive summary statistics for serum Ab values including median, minimum, and maximum will also be provided.

The GMFR of serum Ab values with its 95% CI at 28 days after the second dose of IP over baseline (pre-Dose 1 of primary series) will be provided. Its 95% CIs will be calculated based on the t-distribution of the log-transformed values then back transformed to the original scale for presentation.

The number and percentage of participants with seroresponse due to vaccination will be provided with 2-sided 95% CI using Clopper-Pearson method at 28 days after the second dose of IP, where seroresponse at subject level is defined two ways:

- 1. as an Ab value change from baseline (pre-Dose 1 of primary series) below the LLOQ to $\geq 4 \times \text{LLOQ}$, or at least a 4-fold rise if baseline is $\geq \text{LLOQ}$.

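### The GMR hypotheses are decided on a baseline-adjusted ratio that can differ, in either direction, from the ratio of the titres infants and adults actually have

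*SAP*

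**What the plan says.** SAP 6.4.3 compares the Day 85 antibody value in infants with the Day 57 value in P301 adults by ANCOVA, with group "as the fixed variable, adjusted by the baseline serum Ab value". It then states "The GMR (Study P206 vs. Study P301) will be estimated by the ratio of GLSM", and noninferiority "will be demonstrated if the lower bound of the 95% CI of the GMR > 0.667". The superiority (bound above 1) and super-superiority (bound above 1.5) rules use the same GMR, and SAP 6.4.4 carries the method over to HA7 and HA9. A further GMR with a t-based interval is reported in addition. It is not said to be unadjusted, and no conclusion depends on it.

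Protocol 9.5.1 has a group term and adds that "the analysis may adjust for key characteristics such as age, sex, etc"; it does not name baseline antibody. The protocol endpoint compares GMTs, and SAP 4.3 defines the GMR as a ratio of geometric means.

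On infant baselines, Protocol 2.2 describes the antibody that vaccinated mothers pass to their infants: "titers wane over the course of the first 6 months of life and are undetectable in up to 43% of infants at 6 months of" (that is, at half a year old). SAP 5.8 and 6.1 define baseline-negative by RT-PCR and anti-nucleocapsid serology only, so maternal spike antibody from vaccination stays in PPIS-Neg. Under SAP 6.1, "antibody values reported as below LLOQ will be replaced by 0.5 × LLOQ".

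**The concern.** Baseline adjustment is routine in a randomised trial because the arms share one baseline distribution. Here the arms are infants in one study and adults in another, and the covariate may mean different things in each. In infants it can be passive maternal antibody that is waning. In adults vaccinated before Omicron appeared (Protocol 2.2 dates adult authorisation to December 2020 and Omicron's detection to November 2021), the pre-dose Omicron value is probably the imputed constant.

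If so, the slope is estimated from infants alone, parallel slopes cannot be checked, and the model compares the groups at a shared baseline that hardly any adult has. If maternal antibody blunts the response, the infants' GMR is raised; if it persists and adds to the Day 85 titre, the GMR is lowered. HA1 is co-primary and is meant to support inferred effectiveness, so the quantity tested should be the one that the endpoint and the power statement describe.

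**Working it through.** **Inputs from the documents.** About 250 evaluable infants, SD of log titre 1.0 and true GMR 1 (SAP 4.3); lower bound above 0.667 (SAP 6.4.3); 2-sided alpha 0.05 (SAP 4.3). Adult seroresponse rate (SRR) 60–70%, SRR margin 5 points (SAP 4.3).

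**Assumptions, because the documents are silent.** 250 adults; adult baseline constant; infant baseline 2-, 4- or 8-fold above it (D = ln 2, ln 4, ln 8); slope b of log post-dose titre on log baseline from −0.2 to +0.2.

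**1. The plan's power figure.** The SAP states that "there will be at least 90% power to demonstrate noninferiority of the immune response against Omicron variant", "in infant population at a 2-sided alpha of 0.05".
- SE = √(2/250) = 0.0894 and ln(1/0.667) = 0.405.
- Power = Φ(0.405/0.0894 − 1.96) = Φ(2.57) = 99.5%.
- With 250 infants, 90 adults give 91% and 85 give 89.7%.

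The claim is reproduced with about 90 adults or more. It contains no covariate.

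**2. What adjustment does.** With a common slope:

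ln(GMR adjusted) = ln(GMR raw) − b × D

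With a constant adult baseline, SE adjusted = s √(1/n₁ + 1/n₂ + D²/SSx). SSx is the infant baseline sum of squares, and s² averages the adult variance 1 and the infant residual variance 1 − b²SDx².

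**3. One data set.** Observed raw GMR 0.75: lower bound 0.75 × e^(−1.96 × 0.0894) = 0.629, a fail. With D = ln 4 and infant baseline SD 1.0:

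| b | Adjusted GMR | Lower bound | HA1 |
|---|---|---|---|
| −0.2 | 0.990 | 0.776 | pass |
| −0.1 | 0.862 | 0.674 | pass |
| 0 | 0.750 | 0.587 | fail |
| +0.2 | 0.568 | 0.446 | fail |

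The adjusted SE is about 0.125 against 0.089. The result does not always flip: with a 2-fold gap and b = −0.1 the adjusted GMR is 0.804, the lower bound 0.662, and HA1 still fails.

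**4. How often HA1 passes at a true raw GMR of 0.667.** Simulation, 3,000 trials per cell, 43% of infants at the floor:

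| b | 2-fold | 4-fold | 8-fold |
|---|---|---|---|
| −0.2 | 29% | 73% | 97% |
| −0.1 | 10% | 23% | 46% |

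At b = 0 it passes 2.3–2.9% of the time and at b = +0.2 at most 0.1%. The unadjusted rule passes 1.6–3.0% throughout. The rates depend on the baseline shape. With 60% of infants spread from LLOQ to 16 × LLOQ (3.5-fold gap) they are 19% at b = −0.1 and 59% at −0.2; with only 20% of infants above LLOQ they are 6–14%.

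**5. The opposite direction.** At a true raw GMR of 1 and b = +0.2, HA1 power is 20% with a 4-fold gap and 2% with an 8-fold gap, against more than 99% unadjusted.

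**6. Does HA2 catch it?** Take infants below LLOQ at baseline, with no maternal antibody at all. At a raw GMR of 0.667 their SRR is Φ(Φ⁻¹(p) − 0.405), where p is the adult rate.
- p = 60%: Φ(0.253 − 0.405) = 44%, a difference of −16 points.
- p = 70%: Φ(0.524 − 0.405) = 55%, a difference of −15 points.

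Both are far beyond −5 points. Infants with baseline at or above LLOQ need a fourfold rise from their own value under the first SAP definition, which lowers the rate further. With 60% or 100% of infants in the LLOQ to 16 × LLOQ range, infant SRR was 13–37%, and HA2 passed in none of 1,500 trials per cell under either seroresponse definition.

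This protection depends on the 60–70% assumption. At p = 99% the infants below LLOQ would reach Φ(2.326 − 0.405) = 97.3%, a gap of only 1.7 points. No adult rate is given for the original strain (HA9 and HA10).

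**7. Superiority rules.** Observed raw GMR 1.75: lower bound 1.75 × 0.839 = 1.469, so super superiority is not shown. With a 2-fold gap and b = −0.1 the adjusted GMR is 1.75 × 1.072 = 1.876. With SE 0.0994 the lower bound is 1.876 × 0.823 = 1.544, and super superiority is shown.

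**The case against.** The best counter-argument is that HA1 does not stand alone. Superiority opens only after both GMR and SRR noninferiority, and step 6 shows HA2 failing in the favourable-bias cases. A reader might take the 23% or 73% as the trial's false noninferiority rate. The documents do not support that: these are pass rates for HA1 only.

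A reader might also infer that the adjustment simply makes noninferiority easier. That is unsupported too, since neither the slope nor the Omicron baseline gap is given. Protocol 2.2 describes antibody after maternal vaccination, says it wanes, and gives no infant Omicron titres. The gap could be small for Omicron, and the flat adult baseline is an inference.

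Protocol 4.2 speaks of the induced response, and an unadjusted ratio credits any residual maternal antibody to the vaccine. This stands as a cost of the fix. The SAP model does not isolate induction either, because its one slope mixes blunting with carry-over.

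Nor does the SAP clearly contradict the protocol. The protocol's covariate list is open-ended, and SAP Section 1 says the SAP prevails. What remains is that an optional, unnamed covariate became the mandatory decision model without an entry in SAP Section 7.

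Finally, the extra GMR, fold rises and maternal-factor plots might reveal a discrepancy. They do not decide any hypothesis.

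**Conclusion.** The concern holds in both directions. The quantity tested for HA1, HA3, HA5, HA7 and HA9 differs from the ratio of actual titres by slope × baseline gap. Over the ranges examined this can turn a raw GMR of 0.75 into anything from 0.57 to 0.99 with a 4-fold gap. The identity needs only a baseline mean difference and a non-zero common slope. The sizes rest on the assumed slope, gap and baseline shape, on 250 adults, and on adult baselines at the floor.

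The consequences are a wrong HA1 conclusion, a wrong GMR-based superiority or super-superiority conclusion, or loss of the stated HA1 power. HA3 and HA5 formally require HA2 to pass, but the scenario table in SAP 6.4.3 reads its GMR conclusions from the GMR bound alone. A false joint noninferiority claim is not shown under the SAP's own SRR assumption, and the stated power is not miscalculated; it omits the covariate. This should be fixed before any Part 2 analysis. SAP Section 7 reports an enrolment pause but leaves the Part 2 plan in place.

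**What to change.** In SAP 6.4.3, and in 6.4.4 by reference, attach the noninferiority, superiority and super-superiority rules to the unadjusted log-scale GMR with its t-based 95% CI. State that the additional GMR already planned there is this one. Keep the baseline-adjusted GLSM ratio as a labelled sensitivity analysis. Show it with infant and adult baseline distributions, and repeat it in participants of both studies with baseline below LLOQ. Record the change in SAP Section 7.

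The cost is SAP wording and reassignment of a planned output. Any precision gained from the covariate is given up, although in the 4-fold example adjustment widens the interval. Residual maternal antibody at Day 85 will count toward the infant titre; the below-LLOQ analysis checks how much that matters.

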Abbreviations: Ab = antibody; AE = adverse event; AESI = adverse event of special interest; AR = adverse reaction; bAb = binding antibody; CDC = Centers for Disease Control and Prevention; COVID-19 = coronavirus disease 2019; GMFR = geometric mean fold rise; GMT = geometric mean titer; LLOQ = lower limit of quantification; MAAE = medically attended adverse event; mRNA = messenger RNA; RT-PCR = reverse transcriptase polymerase chain reaction; SAE = serious adverse event; SARS-CoV-2 = severe acute respiratory syndrome coronavirus 2; SRR = seroresponse rate; VOC = variants of concern.

Seroresponse is defined as a titer change from baseline (pre-Dose 1) below the LLOQ to ≥ 4 × LLOQ, or at least a 4-fold rise if baseline is ≥ LLOQ.

^{2.} The case definition of COVID-19 includes at least one of the following systemic symptoms: fever (temperature > 38°C/≥ 100.4°F) or chills (of any duration, including ≤ 48 hours); cough (of any duration, including ≤ 48 hours); shortness of breath or difficulty breathing (of any duration, including ≤ 48 hours); fatigue, headache, myalgia, nasal congestion or rhinorrhea, new loss of taste or smell, sore throat, abdominal pain, diarrhea, nausea or vomiting, poor appetite or poor feeding; AND a positive test for SARS-CoV-2 by RT-PCR.

Protocol: mRNA-1273-P206, Original

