In addition, the GMT of antibodies with corresponding 95% CI will be provided at each time point. The 95% CIs will be calculated based on the t-distribution of the log-transformed titer values then back transformed to the original scale. Descriptive summary statistics for GMT including median, minimum, and maximum will also be provided.

The GM fold rise of specific antibodies with corresponding 95% CI at each post-baseline time point over pre-Dose 1 baseline at Day 1 will be provided. The 95% CIs will be calculated based on the t-distribution of the log-transformed values then back transformed to the original scale for presentation.

The number and percentage of participants with seroresponse due to vaccination will be provided with 2-sided 95% CI using the Clopper-Pearson method at each post-baseline time point with Day 28 after the last dose of mRNA-1273.214 primary series being of the primary interest in the analyses, where seroresponse is defined as a titer change from baseline (pre-Dose 1) below the LLOQ to \geq 4 × LLOQ, or at least a 4-fold rise if baseline is \geq LLOQ.

The SRR difference with 95% CI (using Miettinen-Nurminen score method) between infants receiving mRNA-1273.214 primary series in Study mRNA-1273-P206 at 28 days after the last dose of mRNA-1273.214 primary series and adult participants receiving mRNA-1273 primary series in Study mRNA-1273-P301 at Day 57 will be provided.

The noninferiority of seroresponse of mRNA-1273.214 primary series in Study mRNA-1273-P206 compared with mRNA-1273 primary series in Study mRNA-1273-P301 will be considered demonstrated if:

• The lower bound of the 95% CI of the SRR difference is > -5% based on the noninferiority margin of 5%.

Protocol: mRNA-1273-P206, Original

Hypothesis Testing Strategy for Immunogenicity:

The hypothesis tests for noninferiority, superiority, and "super" superiority of mRNA-1273.214 against Omicron as compared to mRNA-1273 primary series against Omicron will be performed sequentially. The noninferiority hypotheses (hypotheses H_A^1 and H_A^2) will be tested first.

Once noninferiority is demonstrated based on both GMT and SRR, superiority (hypotheses H_A^3 and H_A^4) of mRNA-1273.214 as compared to mRNA-1273 primary series will be tested. If the lower bound of the 95% CI of the GMR is > 1, superiority based on GMT is demonstrated; if the lower bound of the 95% CI of the SRR difference is > 0%, superiority based on seroresponse is demonstrated.

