3.1. Primary Endpoints

The primary safety objective for Part 1 and Part 2 will be evaluated by the following safety endpoints:

- Solicited local and systemic adverse reactions (ARs) through 7 days after each injection
- Unsolicited adverse events (AEs) through 28 days after each injection
- Medically attended AEs (MAAEs) throughout the entire study period
- Serious AEs (SAEs) throughout the entire study period
- AEs of special interest (AESIs) throughout the entire study period
- AEs leading to discontinuation from study participation postdose throughout the entire study period

The primary immunogenicity objective to infer effectiveness of the mRNA-1273.214 vaccine for Part 2 will be evaluated by:

- Co-primary Endpoint: geometric mean (GM) value of antibodies (Ab) against SARS-CoV-2 VOC (Omicron) at 28 days after the second dose of mRNA-1273.214 compared with that of the adult participants at Day 57 (28 days after the second dose) in Study mRNA-1273-P301 dosed with mRNA-1273 (100 μg, 2 doses 28 days apart) primary series
- Co-primary Endpoint: seroresponse rate (SRR) against SARS-CoV-2 VOC (Omicron) at 28 days after the second dose of mRNA-1273.214 compared with that of the adult participants at Day 57 (28 days after the second dose) in Study

mRNA-1273-P301 dosed with mRNA-1273 (100 μg , 2 doses 28 days apart) primary series

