6.4.2. Hypothesis Testing Strategy for Immunogenicity

The hypothesis tests for noninferiority, superiority, and "super" superiority of mRNA-1273.214 against Omicron as compared to mRNA-1273 primary series against Omicron will be performed sequentially. The noninferiority hypotheses (hypotheses HA¹ and HA²) will be tested first.

Once noninferiority is demonstrated based on both GMC or GM level and SRR, superiority (hypotheses $\rm HA^3$ and $\rm HA^4$) of mRNA-1273.214 as compared to mRNA-1273 primary series will be tested. If the lower bound of the 95% CI of the GMR is > 1, superiority based on GMC or GM level is demonstrated; if the lower bound of the 95% CI of the SRR difference is > 0%, superiority based on seroresponse is demonstrated.

Once superiority is demonstrated based on both GMC or GM level and SRR, "super" superiority (hypotheses HA⁵ and HA⁶) of mRNA-1273.214 as compared to mRNA-1273 primary series will be tested. If the lower bound of the 95% CI of the GMR is > 1.5, "super" superiority based on GMC or GM level is demonstrated; if the lower bound of the 95% CI of the SRR difference is > 10%, "super" superiority based on seroresponse is demonstrated.

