- 2. as an Ab value change from baseline (pre-Dose 1 of primary series) below the LLOQ to \geq 4 × LLOQ, or at least a 4-fold rise if baseline is \geq LLOQ and <4 × LLOQ, or at least a 2-fold rise if baseline is \geq 4 × LLOQ.

The SRR difference with its 95% CI (using Miettinen-Nurminen score method) between pediatric participants receiving mRNA-1273.214 in Study P206 at Day 85 and adult participants receiving mRNA-1273 primary series in Study P301 at Day 57 will be provided.

The noninferiority of the SRR of mRNA-1273.214 compared with that of mRNA-1273 primary series will be demonstrated if the lower bound of the 95% CI of the SRR difference is > -5%.

The table below lists possible scenarios of GMR and SRR difference results and corresponding immunogenicity hypothesis testing conclusions.

Endpoints	Scenario		Conclusion
GMC or	1	Lower bound of 95% CI of GMR (GMC _{P206} /	Non-inferiority of mRNA-1273.214 in P206
GM level		GMC_{P301} or GM level _{P206} / GM level _{P301}) \leq	as compared to mRNA-1273 100 µg primary
Ratio		0.667	series (PS) in P301 based on GMR is not
			demonstrated

	3	$0.667 < Lower bound of 95\% CI of GMR$ $(GMC_{P206}/GMC_{P301} \text{ or } GM \text{ level}_{P206}/GM$ $level_{P301}) \leq 1$ $1 < Lower bound of 95\% CI of GMR$ $(GMC_{P206}/GMC_{P301} \text{ or } GM \text{ level}_{P206}/GM$	Non-inferior of mRNA-1273.214 in P206 as compared to mRNA-1273 100 µg PS in P301 based on GMR is demonstrated but superiority is not demonstrated. Superiority of mRNA-1273.214 in P206 as compared to mRNA-1273 100 µg PS in P301 based on GMR is demonstrated but "super"
	4	$ evel_{P301}) \le 1.5$ $Lower bound of 95\% CI of GMR$ $(GMC_{P206}/GMC_{P301} or GM evel_{P206}/GM $ $ evel_{P301}) > 1.5$	superiority is not demonstrated "Super" superiority of mRNA-1273.214 in P206 as compared to mRNA-1273 100 μg PS in P301based on GMR is demonstrated
SRR Difference	1	Lower bound of 95% CI of SRR difference $(SRR_{P206} - SRR_{P301}) \le -5 \%$	Non-inferiority of mRNA-1273.214 in P206 as compared to mRNA-1273 100 µg PS in P301 based on SRR difference is not demonstrated
	2	-5% < Lower bound of 95% CI of SRR difference (SRR _{P206} - SRR _{P301}) \leq 0	Non-inferiority of mRNA-1273.214 in P206 as compared to mRNA-1273 100 µg PS in P301 based on SRR difference is demonstrated but superiority is not demonstrated

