Proportion of subjects with fold-rise ≥ 2 , and fold-rise ≥ 4 of serum SARS-CoV-2 specific bAb levels from Visit Day 1 (baseline) at each post injection time points will be tabulated with 2-sided 95% Clopper Pearson CIs.

- GMC of SARS-CoV-2-specific nAb concentrations with corresponding 95% CI will be provided at each time point using the same method mentioned above.
- GMFR of SARS-CoV-2-specific nAb concentrations with corresponding 95% CI will be provided at each postbaseline timepoint over pre-injection baseline at Day 1 using the same method mentioned above.

Proportion of subjects with fold-rise ≥ 2 , and fold-rise ≥ 4 of serum nAb from Visit Day 1 (baseline) at each post-injection time points will be tabulated with 2-sided 95% Clopper-Pearson CIs.

- Proportion of subjects with seroresponse due to vaccination will be tabulated with 2-sided 95% Clopper-Pearson CIs at each postbaseline timepoint. The definition of seroresponse can be found in Section 6.4.2.
- A plot to display the Ab value change from baseline to 28 days after the last dose in each vaccination group against the maternal factors (maternal COVID-19 vaccine status and maternal COVID-19 infection status) stratified by infant baseline SARS-CoV-2 status will be provided.

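### SAP 6.4.3 defines the co-primary seroresponse endpoint two ways and does not say which definition decides the seroresponse-rate tests

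*SAP*

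**What the plan says.** - **Protocol, Table 3 footnote and Section 9.5.1.** There is one definition ("Seroresponse is defined as a titer change from baseline (pre-Dose 1) below the LLOQ to" at least 4 × LLOQ, or at least a 4-fold rise when baseline is at or above LLOQ). Section 9.5.1 repeats it for the analysis.
- **SAP 3.1.** The endpoint is restated as "Co-primary Endpoint: seroresponse rate (SRR) against SARS-CoV-2 VOC (Omicron) at 28 days after the second dose of mRNA-1273.214", without the protocol's footnoted definition.
- **SAP 6.4.3.** The sentence on seroresponse percentages says "where seroresponse at subject level is defined two ways". Definition 1 is the protocol's. Definition 2 keeps the 4-fold requirement for a baseline from LLOQ to below 4 × LLOQ, but adds "or at least a 2-fold rise if baseline is" at or above 4 × LLOQ. Noninferiority on SRR then "will be demonstrated if the lower bound of the 95% CI of the SRR difference is > -5"%, and a single conclusion table follows.
- **SAP 6.4.2.** The superiority rule is "if the lower bound of the 95% CI of the SRR difference is > 0%, superiority based on seroresponse is demonstrated". The super-superiority rule is the same with 10%. Neither names a definition.
- **SAP 6.4.4.** The secondary SRR comparisons (HA8, HA10) use the methods of 6.4.3.
- **SAP 6.4.5.** "The definition of seroresponse can be found in Section 6.4.2", but 6.4.2 contains none.
- **SAP Section 7.** The list of changes from the protocol does not include definition 2.

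**The concern.** Section 6.4.3 is the only place where the SAP defines seroresponse. It gives two definitions and ranks neither. It does not call one primary, and it does not require success on both. Every SRR decision rule downstream refers simply to the SRR difference.

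One of the two co-primary endpoints, and four further SRR hypotheses, could therefore be decided on whichever definition is chosen, and nothing in the SAP stops that choice being made with results in hand. The same data could fall into different rows of the conclusion table.

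**Working it through.** **What the definitions can change.** They differ only for a participant with baseline at or above 4 × LLOQ and a rise of at least 2-fold but less than 4-fold. Every definition 1 responder is also a definition 2 responder, so definition 2 never lowers a group's SRR. The difference between groups can move either way, depending on how many are reclassified in each.

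**Inputs.** From SAP 4.3: about 250 evaluable infants, adult SRR 60–70%, infants 10 points higher, margin 5 points, two-sided alpha 0.05. From SAP 6.4.3: Miettinen-Nurminen interval. Assumed, because the documents do not give them: 250 adults; definition 2 gains of 2 or 5 points in infants and 0 to 2 points in adults.

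**The plan's own figure.** Power = Φ((0.10 + 0.05)/SE − 1.96), with SE = √[p_A(1−p_A)/250 + p_I(1−p_I)/250].
- 60% v 70%: SE = √(0.00096 + 0.00084) = 0.0424; power = Φ(1.58) = 94.2%.
- 70% v 80%: SE = √(0.00084 + 0.00064) = 0.0385; power = Φ(1.94) = 97.4%.

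The stated power of at least 90% is reproduced.

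**Chance of passing each SRR test alone.** Both binomials were enumerated exactly, counting outcomes where the Miettinen-Nurminen lower bound exceeds the margin. The true definition 1 difference is +10 points. Entries are for adult SRR 60% / 70%. The GMR co-primary and the sequential gate are not applied.

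| Definition 2 gain in points, infants / adults | HA2 (> −5%) | HA4 (> 0%) | HA6 (> 10%) |
|---|---|---|---|
| none (definition 1) | 94.1 / 97.3% | 65.2 / 73.7% | 2.5 / 2.5% |
| 2 / 0 | 98.0 / 99.4% | 81.2 / 88.6% | 6.9 / 7.6% |
| 5 / 0 | 99.8 / 100.0% | 95.0 / 98.3% | 22.3 / 27.3% |
| 2 / 1 | 96.7 / 98.9% | 74.4 / 83.1% | 4.2 / 4.5% |
| 5 / 2 | 99.2 / 99.9% | 88.1 / 94.7% | 10.7 / 12.8% |
| 2 / 2 | 94.7 / 98.0% | 66.5 / 76.1% | 2.5 / 2.5% |

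**How often the definitions disagree in the same trial** (400,000 simulated trials, nested definitions; adult SRR 60% / 70%). For HA2: 3.9 / 2.1% with an infant-only gain of 2 points, and 5.7 / 2.7% with 5 points. For HA4, when both groups gain 2 points: 8.8 / 8.7%, although the overall chance of passing hardly moves.

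**Worked lower bounds.** The bound is the d at which (p_I − p_A − d)/√{[p̃_I(1−p̃_I)/n_I + p̃_A(1−p̃_A)/n_A] × N/(N−1)} = 1.96. Here p̃ are the maximum-likelihood rates constrained to differ by d, and N = n_I + n_A.

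| Infants v adults (of 250 each) | Lower bound | Result |
|---|---|---|
| 175 v 150 (planned rates) | +1.63% | HA2 and HA4 pass |
| 180 v 150 | +3.70% | unchanged |
| 168 v 162 | −5.91% | HA2 fails |
| 173 v 162 (5 more infants) | −3.85% | HA2 passes |
| 173 v 165 (3 more adults too) | −5.01% | HA2 fails |

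**False-positive side.** Take a true definition 1 difference of exactly −5 points (infants 60%, adults 65%, 250 each; 200,000 simulated trials with Wald limits). Definition 1 alone passes in 0.026. Accepting a pass on either definition gives 0.07 with an infant-only gain of 2 points and 0.22 with 5. These rates are relative to definition 1 as the intended endpoint.

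**The case against.** The strongest reply is that the two documents together already settle the matter. The protocol attaches definition 1 to the co-primary endpoint. Protocol Section 9 requires an amendment to change the primary hypotheses or their methods, and SAP Section 1 confines the SAP to changes that are not principal. On those rules definition 2 could only be supportive. Definition 1 is also listed first, and a switch away from it would be a visible departure from the protocol.

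This makes definition 1 the probable intention. It does not close the gap: SAP Section 1 also says the SAP prevails where its methods differ from the protocol, the SAP does add a definition, and Section 7 does not record it. That the wording sits in the sentence on descriptive percentages does not help either, because the SAP would then give no definition for the test.

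The objections on size largely stand. The gains and the adult sample size are assumptions. The rises in HA4 and HA6 occur because definition 2 was given a larger true difference, and they ignore the gate. With equal gains HA6 does not move. At the planned rates no conclusion changes in the worked example, and HA2 flips only nearer the margin. Relevance is also limited for now: the SAP reports an enrollment pause with 18 participants in Part 1 Arm 2, and Part 2 depends on the Part 1 dose selection. Even so, the SAP does not withdraw Part 2.

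**Conclusion.** The concern holds. The SAP leaves open which definition decides HA2, HA4, HA6, HA8 and HA10, and the same data can give opposite conclusions on a co-primary endpoint. For HA2 at the planned difference, that happens in 2–6% of trials if definition 2 adds 2 or 5 points in infants only. The exposure is larger for HA4 and HA6, and for HA2 near the margin. Neither the direction nor the size of the shift is established, since no baseline titres are given and any reclassification of adults reduces it. No figure was computed for HA8 or HA10. The plan's power statement is not at fault, provided its SRR assumptions refer to the deciding definition. This should be fixed before Part 2 data are unblinded. It has no bearing on Part 1, which tests no hypothesis.

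**What to change.** Before any Part 2 unblinding:

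1. In SAP 6.4.3, state that definition 1, the protocol's, alone decides HA2, HA4, HA6, HA8 and HA10, and label definition 2 supportive.
2. List definition 2 in SAP Section 7 as an addition to the protocol.
3. Correct the cross-reference in SAP 6.4.5 from 6.4.2 to 6.4.3.

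The cost is a few sentences of SAP text. Both definitions are still reported, and sample size and alpha do not change. The sponsor gives up the option of relying on the more lenient definition. A protocol amendment is needed only if the sponsor wants definition 2 to decide.
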